Date	7-26-2018
Title	Is Self-discontinuation of a transurethral catheter following pelvic reconstructive surgery as effective as office-based discontinuation?; A Randomized Controlled Trial
Principal Investigator	[name]
Sub-Investigators	[name]; [name]; [name] MSc; [name], DO; [name], [name]
Research Specialist	[name], MS
Department	Department of OB/Gyn, Division of Urogynecology and Reconstructive Pelvic Surgery
Hatton #	16-075

Purpose of Study:

- To determine if self-discontinuation of transurethral foley catheters in patients diagnosed with postoperative urinary retention (POUR) following inpatient pelvic organ prolapse surgery is non-inferior to office-discontinuation.
 - **Primary Aim:** To determine the incidence of POUR (as defined as the continued need for catheterization) at postoperative day 6-8 (POD6-8) following inpatient pelvic organ prolapse surgery in patients who self-discontinue their indwelling urinary catheter compared to those who present to the office for discontinuation.
 - **Secondary Aims:** To compare patient satisfaction, number of patient related encounters (emergency room, office visit, or telephone calls), incidence of postoperative urinary tract infection (UTI), post void residual volume (PVR) at 2-week postoperative visit, and total duration of catheter use between the two groups.

Hypothesis or Research Question

- We hypothesize that self-removal of indwelling urinary catheters will be non-inferior to office-removal on POD6-8 regarding ongoing symptoms of POUR following inpatient pelvic organ prolapse surgery.
- We further hypothesize that self-removal of indwelling urinary catheters will result in fewer office visits and improved patient satisfaction in the immediate postoperative period.
- In addition, we hypothesize that the duration of POUR (number of days urinary catheter use is required) will be equivalent in the self-removal group compared to that of the office-removal group.
- Lastly, we hypothesize that there will be less incidence of UTI in the self-removal group.

Background

Postoperative urinary retention (POUR) is a common issue following urogynecologic surgery, with incidence rates of 1.4-43% [1-5]. The wide range of incidence is due to the lack of a

standardized definition of POUR. Generally speaking, POUR can be characterized by any impairment in bladder emptying following surgery. While the gold standard for assessing voiding function remains measurement of a postvoid residual (PVR), there are many voiding trial (VT) methods being used across institutions [6]. In our clinical practice, rates of POUR following pelvic reconstructive surgery are approximately 54% [7]. These patients are provided an indwelling transurethral foley catheter to remain in place for approximately one week, at which time they are seen in the office for a subsequent voiding challenge. The incidence of POUR, and continued need for indwelling urinary catheter, at one-week postoperative is approximately 16% (review of prior data from pooled studies of our patients).

Historically, the most widely accepted postoperative VT for the assessment of voiding function was the backfill method. This method consists of retrograde-filling the bladder through the patients foley catheter with 300 mL sterile normal saline (or maximum capacity, if sooner), removing the indwelling urinary catheter, and allowing the patient to void. A voided volume of at least 200 mL (or two-thirds of the instilled volume) is considered passing, and correlates with adequate bladder function. An alternative assessment of voiding function is the spontaneous VT, where the indwelling catheter is removed and a patient is asked to void spontaneously when she has the urge. A PVR is then measured, either by way of ultrasound or with in-and-out catheterization.

It is controversial which of these methods are superior, and studies are conflicted. In a comparison of backfill VT versus spontaneous VT in patients undergoing outpatient urogynecologic surgery, the backfill method was superior in 'passing' rates [8]. However, a recent retrospective study of 1153 patients following urogynecologic surgery showed that backfill VT was associated with an increased rate of urinary tract infections and higher failed trial of void [9]. Furthermore, patient satisfaction does not differ between the two types of VT performed [8]. Nevertheless, both of these methods were studied in a clinical setting, and we lack information on self-discontinuation efficacy at home.

What is evident in all research is that evaluation and management of POUR can be cumbersome, and highly concerning to patients. Patients with indwelling urinary catheters often feel anxiety, embarrassment, and loss of dignity. Furthermore, it has been shown that patients would prefer to be more involved in the decisions around catheter use [10]. Managing an indwelling urinary catheter and returning to the outpatient clinic only a week after discharge from the hospital can be overwhelming for patients and their involved caregivers.

Review of the literature reveals no studies to date regarding self-removal of indwelling urinary catheters. Given the low incidence of POUR at one-week postoperative and patient dissatisfaction with urinary catheter management, home self-removal of indwelling urinary catheters is an important topic of investigation. We aim to fill this knowledge gap by determining the incidence of POUR at POD6-8 with self-removal of indwelling urinary catheters compared to office-removal in the setting of inpatient pelvic organ prolapse surgery. Furthermore, we aim to compare patient satisfaction with self-removal versus office-removal, as previous publications suggest that patients may feel empowered by being more involved in the management of their urinary catheter [10]. If self-removal proves to be non-inferior to

office-removal, this would be a new, efficient and potentially cost-effective management option for POUR.

Research Plan

- **Study Design**
 - Randomized controlled trial
 - Non-inferiority trial

- **Setting for the study**
 - Patients of Cincinnati Urogynecology Associates, TriHealth Inc, undergoing inpatient surgery for pelvic organ prolapse at Good Samaritan Hospital or Bethesda North Hospital who fail their voiding trial will be offered enrollment.
 - Those patients who choose to enroll in the study will be provided with a sealed envelope that will dictate to which group the patient has been randomized.
 - Those patients randomized to the self-removal group will be provided with a diagrammatic handout, illustrating proper removal of their catheter. They will be instructed to remove their indwelling urinary catheter at home on the morning of POD7. They will also be provided with the direct phone number of our Research Nurse and the pager number of our on-call staff, which they will use to contact the team if they are unable to void within 5 hours of catheter removal. If they are unable to void, the Research Nurse or on-call staff will arrange a clinic visit for the same day at one of three outpatient clinics (Clifton, West Chester, Kenwood) for replacement of an indwelling urinary catheter.
 - Those patients randomized to the office-removal group will schedule an office visit for POD6-8 at one of three outpatient clinics (Clifton, West Chester, Kenwood). At this visit the patient will undergo a backfill VT.
 - All patients will present to one of three outpatient clinics (Clifton, West Chester, Kenwood) at two weeks postoperative for a routine postoperative evaluation, measurement of PVR, urine dip, and completion of the patient questionnaire.
 - All patients will present to one of three outpatient clinics (Clifton, West Chester, Kenwood) at six weeks postoperative for a routine postoperative evaluation and urine dip.

- **Participants**
 - Study population: All women 18 years of age or older, who undergo vaginal vault suspension or robot-assisted laparoscopic sacrocolpopexy, with or without additional concomitant procedures by a physician at Cincinnati Urogynecology Associates, TriHealth for treatment of pelvic organ prolapse (POP) and who fail their VT prior to discharge will be approached for recruitment.
 - Inclusion/Exclusion criteria:

- Inclusion
 - Adults 18 years of age or older
 - Undergoing vaginal vault suspension or robot-assisted laparoscopic sacrocolpopexy by a physician at Cincinnati Urogynecology Associates, TriHealth for the treatment of POP
 - Concomitant procedures such as hysterectomy, suburethral sling, anterior or posterior colporrhaphy, bilateral salpingectomy or salpingoophorectomy
 - Failed voiding trial prior to discharge
- Exclusion
 - Unwillingness to participate in the study
 - Physical or mental impairment that would affect the subject's ability to self-remove indwelling urinary catheter, including patient's with Multiple Sclerosis, Dementia, Parkinsonism, or those who have impaired mobility or are wheelchair bound
 - Bladder injury, fistula repair or other need for prolonged catheterization
- Sample size
 - A sample size was calculated to be 74 patients in each arm based on the following:
 - The estimated POUR requiring indwelling urinary catheter at 7 days postoperative is 16% (based on internal audit of data)
 - The non-inferiority margin was set at 15%. [11]
 - The power was set at 80%.
 - Due to estimated loss-to-follow-up rate of approximately 13%, the number of patient enrollment was set at 84 subjects in each group, 168 total.
- **Data Collection**
 - Primary outcome:
 - POUR at POD6-8 as defined by need for continued indwelling urinary catheter or intermittent self-catheterization.
 - Continued indwelling urinary catheter will be required in the following settings:
 - Self-removal group – inability to void or sense of incomplete bladder emptying after 5 hours of catheter removal
 - Office-removal group – voided volume less than two-thirds of the instilled volume or PVR greater than 100mL after backfill of up to 300mL

- Secondary outcomes
 - Scores on patient questionnaire collected at the two-week postoperative visit [12,13] (Patient Questionnaire and Visual Analog Scale)
 - Number of patient contact points (office visits, telephone calls and emergency room visits) regarding POUR or indwelling urinary catheter care up to 2 weeks postoperative.
 - PVR measurement at 2-week postoperative visit.
 - UTI diagnosed within 6 weeks postoperative (as defined by positive urine culture, or treatment with antibiotics by a provider).
 - Total duration (number of days) of urinary catheter use (including indwelling urinary catheter and intermittent self catheterization) within 6 weeks postoperative.
- General demographic data
 - Name, date of birth, age, race, weight, height, BMI, parity, tobacco use, medical comorbidities, date of surgery
- Data collection tool
- **Intervention or experimental aspect of the study**
 - Procedure
 - All patients of Cincinnati Urogynecology Associates who undergo vaginal vault suspension (VVS) or robot-assisted laparoscopic sacrocolpopexy (RSCP) will have a backfill VT on POD1 at 6am, per standard practice. The backfill VT will be performed by the nursing staff. Per protocol, up to 300ml sterile saline will be instilled into the bladder and the indwelling urinary catheter will be removed. Patients will be allotted 30 minutes to void. The instilled volume, voided volume, and PVR if needed will be recorded.
 - Failure of backfill VT is defined by inability to void two-thirds of the instilled volume or PVR greater than 100mL.
 - Patients who fail the backfill VT postoperatively will have an indwelling urinary catheter reinserted and will be taught on its use by nursing staff. They will be approached for possible study enrollment by one of the study investigators.
 - If a patient agrees to participate in the study, she will receive a sealed envelope dictating to which group she will be randomized.
 - All subjects will be provided prescriptions for pain medication, bowel regimen, and cranberry supplements, per standard practice.

- Number of contact points (office visits, emergency room visits, and phone calls to care team) will be recorded during the first two weeks postoperative.
- Self-removal group
 - They will be provided with a diagrammatic handout, illustrating proper removal of their catheter (Diagram for Self-Removal)
 - They will be instructed to remove their indwelling urinary catheter at home on the morning of POD7 at approximately 7am.
 - They will be provided with the phone number of the Research Nurse and the pager number of the on-call staff.
 - On POD6 evening or POD7 morning, the Research Nurse will contact each patient to remind patients of the plan and review proper self-catheter removal.
 - On POD7 they will discontinue their indwelling urinary catheter by way of the instructions provided.
 - If they are UNABLE to void within 5 hours of catheter removal or have feelings of incomplete bladder emptying, they will call the Research Nurse or page the on-call staff. The Research Nurse or on-call staff will arrange a clinic visit for the same day at one of three outpatient clinics (Clifton, West Chester, Kenwood) for replacement of an indwelling urinary catheter.
 - A urine dip will be performed on the urine collected via the catheter. If positive for leukocyte esterase, white blood cells, or nitrites, the urine sample will be sent to the laboratory for culture
 - All urine culture results will be reviewed and if positive, will be treated and recorded. They will return to home with an indwelling urinary catheter and represent to the office for their two-week postoperative visit.
 - If they are ABLE to void within 5 hours of self-removal, they will remain without a catheter and present for their routine two-week postoperative visit the following week.
- Office-removal group
 - They will call the office to schedule a repeat VT visit on POD6-8 (POD7 will be encouraged).
 - They will have a backfill VT (as described above).
 - If they are UNABLE to void two-thirds of the instilled volume or have a PVR greater than 100ml, they will have an indwelling urinary catheter

reinserted at that time. They will return to home with an indwelling urinary catheter and represent to the office for their routine two-week postoperative visit.

- If they are ABLE to void two-thirds of the instilled volume, they will remain without a catheter and present for their routine two-week postoperative visit the following week.
 - A urine dip will be performed on the foley catheter urine sample prior to the initiation of the backfill VT. If positive for leukocyte esterase, white blood cells, or nitrites, the urine dip will be sent to the laboratory for culture. All urine culture results will be reviewed and if positive, will be treated and recorded.
- Two-week postoperative visit
- All patients will present to the office for routine two-week postoperative visit.
 - Those patients who have an indwelling urinary catheter in place at this time will have a backfill VT performed (as described above).
 - If they are UNABLE to void two-thirds of the instilled volume or have a PVR greater than 100ml, they will either have an indwelling urinary catheter replaced or be taught intermittent self-catheterization. They will have follow-up per standard office practice.
 - If they are ABLE to void two-thirds of the instilled volume, they will remain without a catheter and present for their routine six-week postoperative visit.
 - All patients will have a PVR measured and recorded.
 - All patients will have a urine dip performed (either from a voided urine sample or foley catheter urine sample) at their two-week postoperative visit. If positive for leukocyte esterase, white blood cells, or nitrites, the urine dip will be sent to the laboratory for culture. All urine culture results will be reviewed and if positive, will be treated and recorded.
 - All patients will complete the patient satisfaction questionnaire and VAS at their two-week postoperative visit (Patient Questionnaire and Visual Analog Scale)
 - Six-week postoperative visit All patients will present to the office for routine six-week postoperative visit.
 - All patients will have a urine dip performed at their six-week postoperative visit. If positive for leukocyte esterase, white blood cells, or

nitrites, the urine dip will be sent to the laboratory for culture. All urine culture results will be reviewed and if positive, will be treated and recorded.

- Total duration of catheter use (indwelling urinary catheter or intermittent self-catheterization) will be extracted from the patients' chart and recorded at this time.

Statistical Analysis

- Descriptive statistics will be generated for demographic information such as age, race, BMI, Parity etc. The OR and 95% CI's of OR will be utilized to compare our primary outcome, the incidence of POUR between the two groups (self-removal and office-removal). Continuous variables such as the patient satisfaction questionnaire on VAS will be analyzed using independent samples t-tests or Mann-Whitney U test for significant difference between groups. Categorical variables will be tested using the Fisher's exact or Pearson Chi-square tests.

Ethical Considerations

- **Informed consent**
 - Patients who agree to participate in the study will sign a written informed consent. They will be consented by one of the stated investigators or trained Research Nurse and they will receive a copy of the signed informed consent statements (ICS). A copy will be put in their medical file.
- **Privacy information**
 - Extensive efforts will be made to ensure and maintain participant confidentiality. All identifying information will be maintained in a secure area at all times. Source documentation will be maintained in a separate folder. When documentation has to be made available for data analysis, copies of the source (Excel spreadsheets) with only Subject ID number visible and personal information obscured will be used. All communication between staff members regarding participant data will occur via the Subject ID number only. However, identifying information will be retained in the original/source documents.
 - The participant will be logged in the Excel spreadsheet and assigned a Subject ID number. Each participant will be assigned the next available Subject ID number. Once each Subject ID number has been assigned, it will not be reassigned. The Excel spreadsheet will be stored on a password

protected, encrypted TriHealth computer for ten years following study closure, and then purged.

Cost/Budget

Item	Amount	Qty	Total
Patient stipend for visit (mileage, time for travel, questionnaire completion, etc)	\$25.00	168	\$4,200.00

Estimated Period of time to complete study:

Estimated Period of Time to Complete Study	

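### Catheter duration is hypothesised to be equivalent between arms, but the only analysis rule that covers it is a test for difference, which cannot show equivalence

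*Combined protocol and SAP*

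**What the plan says.** - **Hypothesis or Research Question, third bullet:** the duration of retention, counted in days of catheter use, "will be equivalent in the self-removal group compared to that of the office-removal group".
- **Purpose of Study, Secondary Aims:** the aim is only to compare several outcomes, "and total duration of catheter use between the two groups".
- **Data Collection, Secondary outcomes:** "Total duration (number of days) of urinary catheter use", indwelling or intermittent, within six weeks of surgery. No standard deviation is given.
- **Statistical Analysis:** the primary outcome gets an odds ratio with a 95% CI. Continuous variables, with the satisfaction VAS as the example, "will be analyzed using independent samples t-tests or Mann-Whitney U test for significant difference between groups". Categorical variables get Fisher's exact or chi-square tests. Duration is not named, so it falls under the rule for continuous variables.
- **Sample size:** the only margin in the document is here ("The non-inferiority margin was set at 15" percent), and it belongs to the retention rate.

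**The concern.** A t-test or Mann-Whitney test takes no difference as its null hypothesis. A small p-value contradicts equivalence, but a large one does not establish it, because it can also come from too few patients or too much spread. Demonstrating equivalence requires a stated largest acceptable difference and an interval that lies inside it. The plan has neither for catheter-days.

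The only result of the planned test that could be offered in support of the third hypothesis is therefore a non-significant one. The primary comparison does not fill the gap: it concerns a proportion at postoperative day 6 to 8, not days accumulated over six weeks. At stake is a secondary claim that self-removal leaves catheter time unchanged, made from data that may be compatible with a difference of a day or more per patient.

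**Working it through.** **1. Reproduce the plan's own figure.** Inputs from the Sample size section: 16% retention in both arms, margin 15 percentage points, power 80%. Alpha is not stated. With one-sided 0.05:

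n = 2 × 0.16 × 0.84 × (1.645 + 0.842)² / 0.15² = 73.9, so 74 per arm.

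This matches. One-sided 0.025 would give 94. The 74 belongs to the primary outcome; no calculation was made for duration.

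**2. A simple model for duration.** Under the procedures for both groups, a patient who fails at day 6 to 8 goes home with a catheter until the two-week visit. Take 7 days for success and 14 for failure. The 7-day step follows the visit schedule; the two-point simplification is an assumption.

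**3. Chance of missing a real difference.** Take 31% v 16%, the gap equal to the primary margin, with 74 per arm.

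- Mean difference = 7 × (0.31 − 0.16) = 1.05 days
- SE = 7 × √[(0.16 × 0.84 + 0.31 × 0.69)/74] = 0.480 day
- 1.05/0.480 = 2.19, so two-sided 5% power = Φ(2.19 − 1.96) = 0.59
- Missed: about 41%

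In simulation the t-test misses about 42%. Mann-Whitney misses about 42% if every office removal is on day 7, and 53 to 55% if office removals fall on days 6/7/8 in proportions 15/70/15. That scatter is an assumption; the plan says only that day 7 is encouraged.

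**4. Add a long tail.** The two-week procedures allow further catheterisation after a second failure. Assume that 16% or 30% of failures last 21, 28 or 42 days with equal chance. These durations exceed 14 days by 7, 14 or 28, on average 16.33.

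| Share extended | Extra days per failure | Mean difference, 31% v 16% | t-test misses | Mann-Whitney misses |
|---|---|---|---|---|
| 16% | 7 + 0.16 × 16.33 = 9.61 | 0.15 × 9.61 = 1.44 | 58–61% | 42–55% |
| 30% | 7 + 0.30 × 16.33 = 11.90 | 0.15 × 11.90 = 1.79 | 60–62% | 42–55% |

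The ranges cover the analytic and simulated results with and without scatter.

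**5. What an interval could show at 74 per arm.** Take 16% in both arms and a true difference of zero.

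- No tail: SD = 7 × √(0.16 × 0.84) = 2.57; SE = 2.57 × √(2/74) = 0.422; 95% half-width = 1.96 × 0.422 = 0.83 day.
- With the tails above: SE about 0.74 and 0.92; 95% half-widths about 1.4 and 1.8 days.
- Two one-sided tests (TOST) at 5%, with an illustrative margin of 15 points × 7 days = 1.05 days and no tail: power = 2Φ(1.05/0.422 − 1.645) − 1 = 2Φ(0.844) − 1 = 0.60.
- With a tail, the 90% half-width is 1.645 × 0.74 = 1.21 days or more. That exceeds 1.05, so power is essentially zero.

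**The case against.** The case on the other side has several parts.

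- **Intent.** No section says how a non-significant duration result will be interpreted, and the Secondary Aims promise only a comparison, which a difference test fits. In a short investigator protocol, equivalence may loosely mean that no difference is expected. This stands in part: the misreading is a risk, not a stated plan. But the hypothesis is written as equivalence and the plan offers no other way to address it.
- **Likelihood of a non-significant result.** A reader might infer that the trial would probably report p > 0.05 when self-removal adds a day. The figures do not support that. In the simple model the t-test detects 1.05 days about 59% of the time, and Mann-Whitney passes a 50% miss rate only under an assumed scatter.
- **Choice of test.** A reader might infer that Mann-Whitney is unusually poor for this outcome. It loses to the t-test when there is office-day scatter and no long tail, but does better once some failures run to several weeks, which the plan allows for.
- **Small differences.** A reader might add that smaller differences, such as 0.7 day, are missed even more often. Against a margin of about one day, those arms would count as equivalent, so non-rejection would not lead to a wrong conclusion there.
- **Importance.** The outcome is secondary and unpowered. This stands, and it limits the weight of the point.

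**Conclusion.** Wrong as written: the planned test does not match the stated hypothesis. That conclusion rests on the text alone and needs no assumption about spread.

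The size is illustrative, because the documents give no standard deviation, tail or scatter for duration. At 74 per arm, a true difference of about one day is missed by the t-test about 41% of the time, and differences of 1.4 to 1.8 days about 58 to 62% of the time if some failures continue to 3 to 6 weeks. So a non-significant result would be weak evidence that the arms are alike; it is not established that such a result is the likely one. The primary non-inferiority conclusion and the 74 per arm are untouched.

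**What to change.** 1. In Hypothesis or Research Question, restate the duration hypothesis as estimation: the trial will estimate the difference in catheter-days between the arms.
2. In Statistical Analysis, name the outcome. Report the difference in mean catheter-days within six weeks, self-removal minus office-removal, with a 95% CI obtained by bootstrap, because values will clump near days 7 and 14 with a possible long tail.
3. State there that a non-significant test will not be described as equivalence.
4. If the sponsor wants to keep an equivalence claim, it must fix and justify a margin in days before analysis and judge the 90% CI (TOST) against it. The documents supply no such margin; the 1.05 days used above is only an illustration.

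**Cost.** Wording only, with no new data or patients. The price of the estimation route is giving up the equivalence claim. The price of the other route is a high chance of not showing it: at a margin of about one day, power is about 60% at best and essentially zero with a long tail.

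### The primary outcome compares re-catheterization under two different triggers, with no check on self-removal patients who do not call, so it cannot carry the hypothesis about ongoing POUR symptoms

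*Combined protocol and SAP*

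**What the plan says.** The combined protocol and SAP gives one primary outcome label under Data Collection: "POUR at POD6-8 as defined by need for continued indwelling urinary catheter or intermittent self-catheterization". The Primary Aim likewise defines POUR as continuing need for catheterization.

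The same section then sets a separate trigger for each arm:
- Self-removal: "inability to void or sense of incomplete bladder emptying after 5 hours of catheter removal".
- Office removal: "voided volume less than two-thirds of the instilled volume or PVR greater than 100mL after backfill of up to 300mL".

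Under Self-removal group, the patient must call or page staff if she has a problem. The only scheduled staff contact there is a reminder on the evening of POD6 or the morning of POD7. The office arm has a backfill trial at a POD6-8 visit.

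The hypothesis is worded differently from the aim. It expects self-removal to be "non-inferior to office-removal on POD6-8 regarding ongoing symptoms of POUR".

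Other capture exists. Office visits, emergency visits and calls are recorded to two weeks. Everyone has a PVR at the two-week visit, and anyone still catheterized then has a backfill trial. Days of catheter use are extracted from the chart at six weeks. The Statistical Analysis section plans an OR with its 95% CI for the primary outcome. It does not say how an unknown POD6-8 status is scored.

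**The concern.** The office trigger uses no symptoms and the self-removal trigger uses no volumes. The outcome therefore puts neither symptoms nor emptying on a scale common to both arms at POD7, although the Background section regards PVR as the reference standard for voiding function.

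Ascertainment also differs. An office patient who attends has a recorded result. A self-removal patient who does not call has no recorded POD7 voiding, and under the plan she passes as a success. In a non-inferiority trial, failures missed in the new arm make the arms look more alike or favour the new arm. Symptom reports from patients who are emptying well push the other way.

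At stake is a report of non-inferiority on symptoms when the trial has compared re-catheterization under two triggers, with nothing to show how far that result depends on patients who did not call.

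**Working it through.** **1. The plan's own sample size.** Inputs from the Sample size section: 16% failure (taken for both arms), margin 15% (read as percentage points, since the scale is not stated), power 80%. Alpha is not stated.

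n per arm = 2 × 0.16 × 0.84 × (z_α + 0.842)² / 0.15²
- One-sided 5%: 73.9, which rounds up to the stated 74.
- One-sided 2.5%: 93.8, rounding up to 94.

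The design figure matches one-sided 5%, but the analysis section names a 95% CI. Both levels are shown below because the plan does not name the deciding interval.

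**2. How many unrecorded failures change the answer.** Assume 74 analysed per arm and 12/74 = 16.2% failures in each. Wald upper limit for the risk difference = d + z × √[p_S(1−p_S)/74 + p_O(1−p_O)/74].

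At 12 v 12: d = 0 and SE = √(2 × 0.1622 × 0.8378 / 74) = 0.0606. The limit is 1.645 × 0.0606 = 10.0 points, or 1.960 × 0.0606 = 11.9 points, so non-inferiority is declared. Now count some presumed self-removal successes as failures:

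| Self-removal v office | One-sided 5%, Wald | 95% CI, Wald | 95% CI, score |
|---|---|---|---|
| 14 v 12 (2 rescored) | 13.0 | 14.96 | 15.04 |
| 15 v 12 (3 rescored) | 14.5 | 16.5 | 16.5 |
| 16 v 12 (4 rescored) | 16.0 | 18.0 | 18.0 |

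The score column combines Wilson limits. At 14 v 12: 0.0270 + √[(0.2929 − 0.1892)² + (0.1622 − 0.0953)²] = 0.1504.

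Non-inferiority is lost with 4 rescored patients at one-sided 5%. With a 95% CI it is lost with 2 (score) or 3 (Wald). For scale, the plan allows 84 − 74 = 10 patients per arm for loss to follow-up.

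**3. How far this depends on the scenario.** Suppose the self-removal trigger detects a fraction s of volume-defined failures with no false positives, and the office result is taken as correct. Corrected self-removal rate = p_S/s, with standard error scaled by 1/s. Detection at which the limit reaches 15 points:

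| Observed self-removal v office | One-sided 5% | 95% CI |
|---|---|---|
| 12/74 v 12/74 | 81% | 88% |
| 8/74 v 12/74 | 58% | 63% |

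Check at 12 v 12, s = 0.81: 0.1622/0.81 − 0.1622 = 0.0380; SE = 0.0428 × √(1/0.81² + 1) = 0.0681; 0.0380 + 1.645 × 0.0681 = 0.150.

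**4. Either direction is possible.** These are exact binomial probabilities of declaring non-inferiority with 74 per arm, one-sided 5% and a 16% office rate.
- True volume-defined self-removal failure at the margin (16% + 15 = 31%): the probability is 5% with full detection. With 70% detection (recorded rate 0.7 × 31% = 21.7%) it is 43%.
- True rates equal at 16%, full detection, but 5% of adequately emptying women report incomplete emptying (recorded rate 16% + 0.05 × 84% = 20.2%): power falls from 81% to 53%.

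All detection and false-positive rates in steps 3 and 4 are assumptions; the documents give none. Both steps concern volume-defined retention, which is not the plan's primary outcome.

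**5. Wording that decides who is a failure.** Under Setting for the study, the reason to call is inability to void. The primary outcome definition and the Self-removal group procedure add incomplete emptying. The same procedure also says that a patient able to void within 5 hours stays without a catheter. A patient who voids within 5 hours but feels incompletely empty fits both branches.

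In the office arm, failure includes a PVR above 100 mL, but the pass branch mentions only voiding two-thirds, and the described backfill trial records PVR only as required ("The instilled volume, voided volume, and PVR if needed will be recorded"). This gap is small: voiding two-thirds of at most 300 mL leaves at most 100 mL of instilled fluid, so the criteria diverge only if there is further urine in the bladder.

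**The case against.** The strongest reply is that this is a pragmatic comparison of pathways. The Primary Aim and the outcome definition agree on continued need for catheterization, and different triggers follow from testing removal without a clinic visit. That stands: the outcome is legitimate for the aim as written. The overreach is in the hypothesis wording.

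Three stronger readings are tempting, and the documents do not support them.
- A reader might infer that the plan sets out to claim non-inferior bladder emptying. No section says so; the Background's broad description of POUR is general context.
- A reader might infer that the design is biased towards self-removal. Missed retention would favour it, false symptom reports would count against it, and backfill itself is not error-free: the Background calls the choice of method controversial and cites a study with more failed trials under backfill.
- A reader might take the detection thresholds as showing where the primary result is lost. They concern volume-defined retention. For re-catheterization under each arm's own trigger, a woman with silent retention and no catheter is not a misclassified event.

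It is also fair that contact points, catheter-days and the two-week backfill trial would reveal some missed events, such as a catheter never removed or one replaced elsewhere. They do not show POD7 voiding in patients who did not call. Finally, step 2 rests on equal observed rates. Starting from 8/74, reaching the same 16/74 would take 8 rescored patients.

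**Conclusion.** The concern holds in a limited form. One label carries a patient-reported, call-dependent trigger in one arm and a measured one in the other, with no contact scheduled after removal until two weeks and no common POD7 measure. Non-callers in the self-removal arm are in effect successes, and the hypothesis about ongoing symptoms goes beyond what is measured.

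The net bias cannot be sized or signed from the documents. As an illustration of fragility only, at 12/74 in each arm with the margin read as a risk difference, 4 unrecorded failures (one-sided 5%), or 2 to 3 (95% CI), would reverse the conclusion. The result is much more robust if fewer self-removal failures are observed. This does not invalidate the trial or its sample size. It is worth fixing because the fix is cheap and changes what the trial can properly conclude.

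**What to change.** 1. State the primary estimand and conclusion as re-catheterization at POD6-8 under each arm's own trigger, and align the hypothesis wording with it.
2. At the existing two-week visit, confirm the removal date, voiding on POD7 and any catheterization elsewhere, using the contact and catheter-day records already collected. Treat unconfirmed POD6-8 status in either arm as missing, not as success. Add a worst-case sensitivity analysis judged by the same interval as the primary test, and name that interval.
3. Optionally, pre-specify a misclassification analysis over assumed detection and false-positive ranges in both arms. Label it as supportive and as addressing a different quantity, volume-defined retention, not as a test of the primary result.
4. Report the two-week PVR by arm with a 95% CI as supportive only. It cannot recover POD6-8 status.
5. Reconcile the Setting, primary outcome and Self-removal group texts on a patient who voids within 5 hours but feels incompletely empty, because they decide who counts as a failure. Make the office-arm pass and fail wording consistent too, though it will rarely change a classification.

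Cost: protocol and SAP wording, a few questions at an existing visit and a little more analysis work, with no extra visit or procedure. The downsides are a narrower claim and about one week of recall for POD7 events. None of these changes measures POD7 emptying in the self-removal arm; they keep the conclusion within what is measured.
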